14.1 Confidentiality

The data collected will be data typical for the procedure(s) when performed on eyes outside the study. Any data collected will become part of the patient's clinical record. The data will be subject to the same privacy and confidentiality as other data in the clinical record.

Only the principal investigator, research consultant and clinic staff will have access to the data collected. All data shared outside the practice will be de-identified; patients' protected health information will not be available and will not be reported in any analyses or publications. No data will be sold to third parties. De-identified data may be used for future research.

15. STANDARD EVALUATION PROCEDURES

Table 15.1. Proposed Visits and Study Assessments
(visits are by patient, with both eyes tested)

Activity	Pre-operative	Operative	Postoperative		
	Visit 1	Visit 2	Visit 3	Visit 4	Visit 5
			1 Day	1 Month	3 Months
Informed Consent	X				
Demographics	X				
General Information: Medical History		X			
Surgery			X		
Manifest refraction	X			X	X
Monocular uncorrected distance VA (6m)	X		X	X	X
Monocular corrected distance VA (6m)	X			X	X
Binocular uncorrected and best- corrected distance VA (6m)				X	X
Binocular uncorrected and best distance-corrected intermediate VA (60cm)				X	X
Binocular uncorrected and best distance-corrected near VA (40cm & 33cm)				X	X
Binocular Distance Corrected Defocus Curve (6m)					X
IOLSAT Patient Satisfaction Survey	X				X
QUVID Visual Disturbance questionnaire	X				X
Monitor for Adverse Events and Device Deficiencies		X	X	X	X
Complete Exit Form ¹					X

¹ Complete Exit Form upon termination of subject participation, or at Visit 5, whichever occurs first.

16. DATA CONFIDENTIALITY

No protected health information (PHI), including the patient's name and date of birth, will be collected; to ensure this, no PHI information is permitted to be entered on any of the Case Report Forms (CRFs). Subjects will only be identified by subject IDs and identities will be removed at the initial visit so that there is no further need to protect or destroy the information. Collected information will only be used for purposes of this study and no information will be sold to third parties. The non-PHI information collected may be used for future research, though there is currently no plan to do so.

17. FINANCIAL AND INSURANCE INFORMATION/STUDY RELATED INJURIES

Every effort to prevent study-related injury will be taken by the Study Doctor and staff. In the event a patient is injured as a direct result of the study while following the Study Doctor's instructions and the study requirements, the patient will be instructed to contact his or her doctor immediately. The Study Doctor is to treat the injured subject as needed for those injuries caused directly by this research study. In the event of injury or illness caused by or occurring during a subject's participation in this research study, all charges for medical care provided to the subject will be billed to his or her insurance company. The Study Doctor or Sponsor does not offer to cover the medical care costs for injuries or illnesses that are not caused directly by the research study. The Sponsor does not offer to provide any other compensation, unless specifically agreed to elsewhere in this document. This information will be provided to each study subject before the start of the study in the consent form.

18. STUDY ENDPOINT CRITERIA

18.1. Patient Completion of Study

If a study patient has completed the final visit (Visit 5) of the study, he/she is considered to have completed the study.

18.2. Patient Discontinuation

Each study patient may voluntarily discontinue the study at any time they choose. Study patients who cannot complete the study for administrative reasons (e.g., non-compliance, failure to meet visit schedule, etc.) will be discontinued from the study. Study patients discontinued during the enrollment phase (prior to surgery) of the study will be replaced.

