9.2. Visits and Examinations

Subjects will participate in seven study visits, one eye per visit for bilateral surgery. Visits will include an uptake visit, two operative visits, and 4 total postoperative visits (Visit numbers 1-5 below). The visit schedule, complete with window and associated

CRF forms, are displayed in Table 9.2-1. Details of each study visit, including testing to be conducted, are provided below.

Table 9.2-1. Visit Schedule

Visit Number	Visit Name	Visit Window	CRF Number
1	Preoperative	-30 to 0 days from surgery	1
2,2a	Operative	0 from surgery	2,2a
3,3a	1 Day Postoperative	1-2 days postoperative*	3,3a
4	1 Month Postoperative	30 (± 10) days postoperative**	4
5	3 Months Postoperative	90 (± 20) days postoperative**	5

* relative to the operative eye

** relative to the date the last eye is operated on

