9.5. Discontinued Subjects

Discontinued subjects are those who do not have an exit visit or who come into the office to be exited prior to the scheduled final study visit. Subjects may be discontinued from the study at any time if, in the opinion of the investigator, their continued participation in the study poses a risk to their health. The reasons for discontinuation include:

- a. Adverse event;

- b. Lost to follow-up;
- c. Subject decision unrelated to an adverse event;
- d. Protocol violation;
- e. Treatment failure;
- f. Other.

To ensure the safety of all subjects who discontinue prior to Visit 5, investigators should assess each subject and, if necessary, advise them of any therapies and/or medical procedures that might be needed to maintain their health. Any changes in medical health and/or use of concomitant medications should also be captured.

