11. SAMPLE SIZE JUSTIFICATION

There is no particularly relevant sample size justification with a single-arm study. It is worth noting that prior studies with between 30 and 35 subjects in any given study group have allowed successful distinctions to be made in the performance of different trifocal IOLs, including PanOptix.³ It is expected that 32 subjects (64 eyes) will provide sufficient data to characterize the clinical performance of the lens. To allow for 10% dropout, 35 subjects (70 eyes) will be enrolled.

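### Section 18.2 can be read to require exit of an implanted subject who misses a visit window but could still be measured, and section 10.2 may then drop the data already recorded

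*Combined protocol and SAP*

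**What the plan says.** Section 18.2 has three parts that matter here. The rule applies to "Study patients who cannot complete the study for administrative reasons". The examples and the consequence follow: "e.g., non-compliance, failure to meet visit schedule, etc.) will be discontinued from the study". Replacement is promised only before surgery: "Study patients discontinued during the enrollment phase (prior to surgery) of the study will be replaced".

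Other sections bear on the same subject:

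- Section 18.1 defines completion: "If a study patient has completed the final visit (Visit 5) of the study, he/she is considered to have completed the study". It states no window and no condition on earlier visits.
- Table 9.2-1 sets the 1-month visit at "30 (± 10) days postoperative" and the 3-month visit at "90 (± 20) days postoperative", both counted from surgery on the last eye.
- Section 9.5 is permissive. Subjects may be discontinued if "in the opinion of the investigator, their continued participation in the study poses a risk to their health". Its list of reasons nevertheless includes protocol violation and treatment failure.
- Section 9.2.6 asks that study examinations be done, where possible, at a premature exit.
- Section 10.1 bases efficacy on eyes with uncomplicated, completed implantation and sets no window or completion condition. Section 10.2 limits its summaries to eyes that complete the study.
- Section 11 gives the allowance for loss: "To allow for 10% dropout, 35 subjects (70 eyes) will be enrolled", against 32 subjects judged sufficient.

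The primary outcome (section 8.1) is binocular distance-corrected near acuity at 40 cm, at 1 and 3 months. The defocus curve is scheduled only at Visit 5 (Table 15.1).

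**The concern.** The lens is permanent and the outcome is a measurement. A missed window or poor compliance is therefore no scientific reason to stop measuring. Section 18.2 nevertheless names both as grounds for exit in mandatory wording, and nothing in the documents keeps such a subject in 3-month measurement. Nor do they say that an out-of-window visit is only a deviation, or how its values are to be used.

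At stake are the 3-month primary value and the defocus curve. If section 10.2 is taken literally, the 1-month value already recorded is at stake too. The loss need not be random: subjects who attend late or comply poorly may differ in acuity or satisfaction from those who stay. In a single-arm descriptive study the summary of those who remain is the result, and no control group exists against which a selective loss would show. Scheduled adverse-event monitoring would also end early for an exited subject.

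**Working it through.** **1. Windows (Table 9.2-1).** 1 month: 30 − 10 = 20 to 30 + 10 = 40 days. 3 months: 90 − 20 = 70 to 90 + 20 = 110 days.

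**2. Three cases set against the text.**

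- *Visit 4 on day 45, Visit 5 possible on days 70–110.* The subject can complete as section 18.1 defines it, so the condition in 18.2 (unable to complete) is not clearly met. Exit is not clearly required.
- *Visit 4 in window, Visit 5 possible only after day 110.* This is a failure to meet the visit schedule at the final visit. Section 18.2 can be read to require exit. Under 18.1 the same subject, if examined, has completed, because no window is stated. The two sections can give opposite answers.
- *Judged non-compliant but still reachable.* Non-compliance is a named ground in 18.2. Section 9.5 says only that discontinuation may occur, and ties it to health risk. Again the two do not match.

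In the second and third cases exit costs the 3-month value. Section 10.1 would keep the 1-month value, whereas section 10.2, read literally, would not, because the eye did not complete.

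**3. The plan's allowance (section 11).** 32 / (1 − 0.10) = 35.6, rounded up to 36; 32 × 1.10 = 35.2, also 36. The stated 35 is within one subject, and nothing below depends on that difference. The tolerable loss is 35 − 32 = 3 subjects, and 3/35 = 8.6%, from all causes together.

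**4. How quickly that allowance is used.** The documents give no rate of late visits or non-compliance, so the rates here are assumptions about total loss. With X ~ Binomial(35, p), fewer than 32 remain when X ≥ 4:

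| Assumed total loss p | P(X ≥ 4) |
|---|---|
| 2% | 0.5% |
| 5% | 9.6% |
| 10% | 46.9% |
| 15% | 79.1% |
| 20% | 93.9% |

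If administrative exits at rate w came on top of the planned 10%, the expected number remaining is 35 × 0.90 × (1 − w): 29.9 for w = 5%, 28.4 for 10% and 26.8 for 15%.

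**5. Effect on precision.** The 95% confidence half-width for a mean, in SD units, is t(0.975, n − 1)/√n: 0.361 at n = 32 and 0.388 at n = 28. That change is small. What matters is which subjects are lost, more than how many.

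**The case against.** The strongest reply is that section 18.2 reaches only patients who cannot complete, and that schedule failure merely illustrates why someone might not. This largely stands. A reader might infer that any late 1-month visit forces exit before the 3-month visit. The documents do not support that, since a subject seen on day 45 can still attend Visit 5 and so complete under 18.1. The reply does not dispose of the subject available only after day 110, or the one judged non-compliant. A site could reasonably exit either.

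A reader might also infer from section 9.5 that poor outcomes are removed as treatment failures. That does not follow. The section is permissive, its list gives reasons for discontinuation and requires no exit, and treatment failure does not appear in 18.2.

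There is mitigation. Section 9.2.6 asks for examinations at premature exit, section 9.5 asks that subjects leaving before Visit 5 be assessed and health changes captured, and section 13.4 provides for follow-up care. To say that all safety follow-up ends would therefore be too strong. An early exit examination, however, is not a 3-month measurement.

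Finally, one might turn an assumed 5–15% of late visits into about 2 to 5 lost subjects (0.05 × 35 = 1.75; 0.15 × 35 = 5.25). That treats every out-of-window visit as an exit, on rates the documents do not give. It is not an estimate of the loss.

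**Conclusion.** The point holds as a defect of wording with a real consequence for the data. Section 18.2 does not plainly require exit for every missed window, but it can be read to require it for implanted subjects who could still be measured, and it fits poorly with 18.1 and 9.5. Combined with the completer restriction in 10.2, it permits avoidable and possibly selective loss of the primary outcome at both time points and of the defocus curve.

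The number affected is unknown. The only figure fixed by the plan is the margin of 3 subjects (8.6%). The probabilities and remaining numbers shown are illustrations at assumed rates, and the effect on precision alone is minor. The conclusion rests on two readings: that a site would apply 18.2 to schedule failure or non-compliance after implantation, and that 10.2 is applied literally.

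**What to change.** - **Section 18.2.** State that, after implantation, a missed or out-of-window visit or other non-compliance is recorded as a protocol deviation, and that outcome and adverse-event collection continues to Visit 5 unless consent is withdrawn or contact is lost.
- **Section 10.2.** Replace the completer restriction with a summary of all available data from implanted eyes at each visit. Report actual days since surgery and add a sensitivity summary restricted to in-window visits.
- **Reconcile sections 9.2.6, 9.5, 10.1, 10.2, 18.1 and 18.2** so that completion, discontinuation and the analysis set mean the same thing throughout. The reasons in 9.5 can stay as recorded reasons for leaving. Its health-based stopping wording needs only to be reconciled with 18.2; no change to that clinical rule is proposed.

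The cost is protocol wording. Some values will fall outside the nominal windows and need a flag, which the in-window summary addresses.

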18.3. Patient Termination

A study patient will be terminated if the study patient develops any severe adverse event that may be related to the study. A study patient will receive appropriate treatment at the discretion of the investigator. Notification of termination will be clearly documented. These study patients are considered to have completed the study and will not be replaced.

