9.2.6. Exit Procedures

In the event of premature exit from the study, all study related examinations should be completed where possible. The Exit CRF should be completed, noting that the subject did not complete the study and the reason for premature study exit. If no premature exit from the study occurs, the Exit CRF should be completed at the end of Visit 5 (Postoperative 3 Months).

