18.5. Study Completion

The study will be complete when all enrolled patients have completed Visit 5 or have been terminated from the study.

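### Section 18.3 makes study exit automatic after any severe, possibly related adverse event and counts the subject as completed, against 9.2.6 and 9.5; small effect, simple wording fix

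*Combined protocol and SAP*

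**What the plan says.** Section 18.3 sets a mandatory rule: "A study patient will be terminated if the study patient develops any severe adverse event that may be related to the study". It adds: "These study patients are considered to have completed the study and will not be replaced".

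The trigger word is defined. Section 12.3.1 (so numbered, but placed within 13.3) calls an event severe when it is incapacitating and also leaves the subject unable to work or carry on usual activities. It sets no minimum duration. Seriousness is defined separately in 13.3, by outcome. Relatedness in 12.3.1 includes events that are only possibly related.

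Other sections treat early exit differently:

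- 9.2.6 has the Exit CRF completed, "noting that the subject did not complete the study and the reason for premature study exit". It also says: "In the event of premature exit from the study, all study related examinations should be completed where possible".
- 9.5 classes as discontinued those "who come into the office to be exited prior to the scheduled final study visit". It lists adverse event as a reason and lets the investigator discontinue a subject whose health is at risk from continuing.
- 18.1 says: "If a study patient has completed the final visit (Visit 5) of the study, he/she is considered to have completed the study".
- 18.5 says: "The study will be complete when all enrolled patients have completed Visit 5 or have been terminated from the study".
- The footnote to Table 15.1 says: "Complete Exit Form upon termination of subject participation, or at Visit 5, whichever occurs first".

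**The concern.** In a drug trial, stopping a subject after a severe reaction usually stops the treatment. Here the treatment is an implanted lens. For a subject with both lenses in place, termination under 18.3 removes the remaining scheduled visits and leaves the exposure unchanged. The visits are lost because of what happened to the subject, so the missing 1- and 3-month values would come from those most likely to have done badly.

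The link to the outcomes is direct. Section 13.1 allows an adverse event to be a symptom. A visual disturbance that meets both parts of the severe definition and is judged possibly related would trigger exit, and visual disturbance is what QUVID measures.

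The completer label adds a second problem. Site staff cannot follow 18.3 and 9.2.6 together for the same subject, and a disposition table built on 18.3 would not show adverse-event attrition.

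**Working it through.** **1. Which sections conflict.** For a subject terminated before Visit 5:

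| Section | Is exit automatic? | Status |
|---|---|---|
| 18.3 | Yes | Completed |
| 9.5 | No, investigator's judgement of health risk | Discontinued |
| 9.2.6 | Not addressed | Did not complete |
| 18.5 | Not addressed | Terminated, listed as an alternative to completing Visit 5 |
| 18.1 | Not addressed | Silent: Visit 5 is sufficient for completion, not stated as necessary |

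The conflicts with 9.5 and 9.2.6 are direct. Section 18.1 is not directly contradicted, because 18.3 in effect adds a second route to completion.

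**2. What is lost, by time of termination** (9.2, Table 9.2-1, Table 15.1).

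- Between Visits 2 and 2a: the second study implantation and all later assessments.
- After the second surgery, before Visit 4: the 1- and 3-month values.
- Between Visits 4 and 5: the 3-month acuity, defocus curve (Visit 5 only), IOLSAT and QUVID, and the 1-to-3-month paired change.
- At Visit 5: little or nothing.

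Table 15.1 shows postoperative QUVID and IOLSAT at Visit 5 only, although 9.2.4 and 9.3.3 also call for them at 1 month. A site working from the table would have no scheduled postoperative questionnaire from a subject who exits before Visit 5.

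The Visit 5 window is 90 ± 20 days after the last surgery, so it opens at day 90 − 20 = 70. An exit examination before day 70 is outside that window.

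**3. The plan's own sample size** (section 11). The inputs are 32 subjects and 10% dropout. 32 / (1 − 0.10) = 35.56, which rounds up to 36. The plan states 35, within one subject. Each exit without a Visit 5 value is 1/35 = 2.9% of enrolment and uses one of 35 − 32 = 3 planned losses.

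**4. Worst case for a rare QUVID category** (Clopper-Pearson 95% intervals). Assume every subject in the worst category at 3 months is terminated before Visit 5 with no usable exit questionnaire.

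| Terminated | With all subjects followed | As reported |
|---|---|---|
| 1 | 1/35 = 2.9% (0.1 to 14.9%) | 0/34 = 0% (0 to 10.3%) |
| 2 | 2/35 = 5.7% (0.7 to 19.2%) | 0/33 = 0% (0 to 10.6%) |

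**5. Mean acuity.** If k terminated subjects are each worse by d logMAR, leaving them out improves the mean by k × d / 35. The values of d are assumed.

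- k = 1: 0.1/35 = 0.003 to 0.3/35 = 0.009 logMAR.
- k = 3: 0.3/35 = 0.009 to 0.9/35 = 0.026 logMAR.

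**6. How often.** The documents give no rate. At an assumed 1% to 5% of subjects, the expected number is 35 × 0.01 = 0.35 to 35 × 0.05 = 1.75. The chance of at least one is 1 − 0.99^35 = 30% to 1 − 0.95^35 = 83%.

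**The case against.** The strongest reply is that the plan already limits the damage.

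- 9.2.6 asks for the study examinations at premature exit where possible.
- 13.4 maintains medical care and relevant follow-up after the study and provides a route for the resulting data.
- 10.1 keeps every enrolled subject in the safety evaluation, and 13.5 tabulates ocular adverse events by type, severity, duration and frequency.

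All of this stands. A reader might infer that the event itself would disappear from the report; these sections rule that out. What they do not supply is a 3-month value from someone who left before the Visit 5 window.

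Second, for a subject between surgeries 18.3 works as a safety stop. That also stands. A reader might infer that exit never changes exposure, but this is true only once implantation is finished. Any replacement wording must keep protection for the second eye.

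Third, a reader might blame 18.3 for uncertainty about who enters the analysis. Section 10.1 defines the efficacy set by uncomplicated completed implantation, with no Visit 5 condition, while 10.2 summarises eyes completing the study. That mismatch affects every early exit. Section 18.3 only adds a conflicting label for one group.

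Fourth, the study is single-arm and mainly descriptive, with no success threshold. Section 11 only expects 32 subjects to be sufficient and disclaims a formal justification, so falling below 32 would breach no stated requirement.

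**Conclusion.** The point holds as a real inconsistency with a small expected effect. Section 18.3 forces exit on intensity and possible relatedness alone, and its completer label conflicts with 9.2.6 and 9.5. If the authors meant serious, the text does not say so, and automatic exit of subjects already implanted would be unhelpful under that reading too.

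The loss is selective, which is why it merits correction despite its size. The shift in mean acuity is minor on the assumed differences: 0.003 to 0.009 logMAR for one exit and up to 0.026 for three. The change from 1/35 to 0/34 is an upper illustration. It requires the only worst-category subject to be the one terminated, with no usable questionnaire at exit, and should not be read as an expected result. The event rates used are assumptions.

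Two stronger conclusions are not supported. The documents do not show that the study's overall findings would be materially changed, and 18.1 cannot be cited as contradicted.

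**What to change.** In 18.3, replace the automatic termination and the completer sentence with:

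> After a severe or serious adverse event that may be related to the device or study procedures, any pending second-eye study implantation is held until the investigator has reviewed the event and recorded the decision. Implanted subjects stay in scheduled follow-up to Visit 5 where possible, unless they withdraw or are discontinued under 9.5. A subject who exits before Visit 5 is recorded as discontinued (9.5), not completed, and is not replaced if already operated on.

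In 18.5, change *terminated* to *discontinued or terminated*. Without this, subjects recorded as discontinued would not count towards study completion.

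Section 13.3 currently sends forms for nonserious events to the Medical Monitor at study close. If the Medical Monitor is to hear of severe nonserious events sooner, add that to 13.3; otherwise leave it out.

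The cost is wording in two sections, or three with the notice step, and a little investigator time per event. No new visit, form or committee is needed. The trade-off is that an automatic stop becomes a hold with investigator review; the investigator can still discontinue a subject for health risk under 9.5.

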12.3.1 Intensity and Causality Assessments

For every adverse event and quality complaint, the investigator must assess the causality as Related or Not Related to the medical device under investigation. An assessment of causality will also be performed by the Medical Monitor utilizing the same definitions, as shown below:

Causality

Related	An adverse event or quality complaint classified as related may be either definitely related or possibly related where a direct cause and effect relationship with the medical device has not been demonstrated, but there is a reasonable possibility that the adverse event or quality complaint was caused by the medical device.
Not Related	An adverse event or quality complaint classified as not related may either be definitely unrelated or simply unlikely to be related (i.e., there are other more likely causes for the adverse event or quality complaint).

Where appropriate, the investigator must assess the intensity (severity) of the adverse event as mild, moderate, or severe based on medical judgment with consideration of any subjective symptom(s), as defined below:

Intensity (Severity)

Mild	An adverse event is mild if the subject is aware of but can easily tolerate the sign or symptom.
Moderate	An adverse event is moderate if the sign or symptom results in discomfort significant enough to cause interference with the subject's usual activities.
Severe	An adverse event is severe if the sign or symptom is incapacitating and results in the subject's inability to work or engage in their usual activities.

The investigator must document any action taken (i.e., medication, intervention, or treatment plan) and outcome of the adverse event or quality complaint when applicable.

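### Section 10.2 ties its summaries to study completers and so can drop 1-month primary data, while 18.3 labels subjects terminated for a severe, possibly related event as completers

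*Combined protocol and SAP*

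**What the plan says.** On the analysis population, section 10.1 bases efficacy on eyes in which surgery was uncomplicated and the lens was implanted. It sets no condition on follow-up, and it evaluates every enrolled subject for safety. Section 10.2 opens by promising a summary at every measurement time point, but its last sentence provides the summaries for eyes that complete the study. Section 8.1 makes binocular distance-corrected near acuity at both 1 and 3 months the primary outcome.

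On who counts as a completer, several sections speak:

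- 18.1: "If a study patient has completed the final visit (Visit 5) of the study, he/she is considered to have completed the study".
- 18.3 requires termination of a subject with a severe event that may be related to the study, and adds: "These study patients are considered to have completed the study and will not be replaced".
- 9.5 counts as discontinued those without an exit visit and those "who come into the office to be exited prior to the scheduled final study visit". Adverse event is reason a in its list.
- 9.2.6 has the Exit CRF completed at a premature exit, "noting that the subject did not complete the study and the reason for premature study exit". It also asks that "all study related examinations should be completed where possible".
- The footnote to Table 15.1: "Complete Exit Form upon termination of subject participation, or at Visit 5, whichever occurs first".
- 18.5: "The study will be complete when all enrolled patients have completed Visit 5 or have been terminated from the study".

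**The concern.** Sections 10.1 and 10.2 describe different populations, and the plan does not say which governs. If 10.2 is followed to the letter, a subject who attends the 1-month visit and then drops out contributes nothing to the 1-month summary. That subject's primary value exists and is valid, and it meets the 10.1 condition.

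The meaning of completing in 10.2 then depends on section 18, where 18.3 gives completer status to one group of early leavers. Two subjects who both leave after the 1-month visit would be handled differently: the ordinary dropout's 1-month value goes, and the terminated subject's value stays. The same terminated subject is a completer under 18.3, a discontinuation under 9.5, and a non-completer on the exit form.

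At stake are a single defined population for the 1-month half of the primary outcome, and a disposition count that agrees with the case report forms.

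**Working it through.** **1. Status of a subject terminated before Visit 5.** 18.3 says completed. 9.5 says discontinued, reason a. 9.2.6 says the exit form notes non-completion, and the Table 15.1 footnote applies that form at termination. These cannot all hold, so the clash of 18.3 with 9.5 and 9.2.6 is direct. 18.1 is softer: it says that attending Visit 5 is enough, not that it is necessary. 18.5 names Visit 5 completion and termination as alternatives, which suggests that they differ but is compatible with 18.3 as administrative closure. A subject terminated at Visit 5 itself raises no conflict.

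**2. How the two clauses interact.** Take 10.2 literally and consider subjects who leave between Visit 4 and Visit 5.

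| Text in force | 1-month value, ordinary dropout | 1-month value, terminated under 18.3 |
|---|---|---|
| 10.2 and 18.3 as written | dropped | kept |
| only 18.3 corrected | dropped | dropped |
| only 10.2 corrected | kept | kept, but label still contradicts 9.5 and 9.2.6 |
| both corrected | kept | kept, label consistent |

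Correcting 18.3 alone would exclude more 1-month data than now. The edits belong together.

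**3. The plan's own figure.** Section 11 wants 32 subjects and allows 10% dropout: 32 / 0.90 = 35.56, or 32 × 1.10 = 35.2, each 36 when rounded up. The plan enrols 35, and 35 × 0.90 = 31.5. The one-subject difference does not matter here. The allowance is 35 − 32 = 3 subjects, and 3/35 = 8.6%.

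**4. Shift in the 1-month mean.** Let m be the ordinary dropouts after Visit 4 whose 1-month values are omitted, and d the amount by which their mean acuity is worse than that of the others. With 35 subjects measured at 1 month:

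shift = (m / 35) × d

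Inputs: m = 0 to 3 (section 11 allowance); d = 0.1 to 0.2 logMAR (assumed; the documents give no value).

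- m = 0: 0.
- m = 3, d = 0.1: 0.0857 × 0.1 = 0.0086 logMAR.
- m = 3, d = 0.2: 0.0857 × 0.2 = 0.0171 logMAR.

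m = 3 requires that all three leave after the 1-month visit and that none is an 18.3 termination, since those stay in under the current text.

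**5. Completion count.** The number k of terminations before Visit 5 is unknown; assume 0 to 3, with no other losses. By attendance at Visit 5, completion is 35/35 = 100%, 34/35 = 97.1%, 33/35 = 94.3% or 32/35 = 91.4%. Under 18.3 it reads 35/35 each time.

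Zero is plausible, because section 12.3.1 sets a high bar: "An adverse event is severe if the sign or symptom is incapacitating". The chance of at least one termination is 1 − (1 − p)^35, which is 16.1%, 29.7% and 65.6% at assumed per-subject rates p of 0.5%, 1% and 3%.

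**The case against.** The strongest reply is that both clauses are loose drafting. Section 10.1 is the explicit definition of the efficacy set. Section 10.2 begins with all time points, does not say only, and may simply mean eyes with data. It already lists the sample size among the continuous summaries, so reporting n at each visit is largely planned. The clause in 18.3 may only close the subject's slot, as the no-replacement wording beside it suggests.

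Much of this stands. Completers-only is the literal reading of 10.2 but not the only one, and the conflict of 18.3 with 18.1 and 18.5 should not be pressed. It does not settle the matter: the plan never says that 10.1 prevails, and the clash with 9.5 and 9.2.6 remains. If closure was the aim, the no-replacement wording already achieves it.

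Three stronger readings are tempting and unsupported:

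- That 18.3 conceals harm. It requires the termination to be clearly documented, the exit form records the reason for a premature exit, and safety covers all enrolled subjects.
- That an inflated completion rate distorts a result. No planned endpoint, test or decision uses a completion rate.
- That terminated subjects lose their 1-month data. Under the current 18.3 they count as completers, so a completers-only 10.2 keeps them. The loss falls on ordinary dropouts, about whom 18.3 says nothing.

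**Conclusion.** The point holds as a minor one. The mismatch between 10.1 and 10.2 affects part of the primary outcome, and the completer label in 18.3 contradicts 9.5 and 9.2.6 for anyone terminated before Visit 5.

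The effect on the 1-month mean is probably small: 0 to about 0.017 logMAR. The upper end assumes three ordinary dropouts, all after Visit 4, each group difference at 0.2 logMAR. Section 11 gives an allowance and not a ceiling; each further such dropout would add at most 0.2/35 = 0.006 logMAR. The termination rates and acuity differences are assumptions.

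The 3-month summaries and the paired 1-to-3-month tests need Visit 5 data in any case, so they are essentially unaffected, as is safety. The completion count would be overstated by exactly the number of terminations before Visit 5, which may be zero.

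**What to change.** Make both edits together, before data are summarised:

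- **10.2:** replace the restriction to completing eyes with: eyes or subjects in the 10.1 efficacy set with data at that visit. Naming subjects as well as eyes matters because the primary outcome is binocular. State n at each visit.
- **18.3:** delete the words that confer completer status, keep the no-replacement rule, and record these subjects as discontinued for an adverse event (9.5, reason a) unless they attend Visit 5. The stopping rule stays as it is, and 18.1 needs no change.

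The cost is one clause and one phrase, with no new subjects, visits or tests. The number analysed will differ between visits, and the completion count may be slightly lower. Section 19.2 links compensation of up to $600 to completing the study, so the sponsor should state that relabelled subjects are not paid less.
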